Specific Aim 2: To determine whether acute calcitriol (vs. placebo) pre-treatment is associated with better performance on a test of attention (e.g., the continuous Performance Task or CPT–IP), after treatment with amphetamine. **Hypothesis:** We hypothesize that healthy human subjects pre-treated with calcitriol will have faster reaction times/higher accuracy on the CPT–IP vs. subjects pre-treated with placebo, after treatment with amphetamine.

Specific Aim 3: As part of a within-subject, two-days, study design, to determine whether acute calcitriol (vs. placebo) pre-treatment is associated with greater amphetamine (Amp)-induced dopamine (DA) release in the caudate, putamen, ventral striatum (VST), and substantia nigra / ventral tegmental area (SN/VTA) of subjects with attention deficit hyperactivity disorder (ADHD). **Hypothesis:** Similar to our hypothesis with healthy controls and congruent with our preliminary findings, we hypothesize that pre-treatment with calcitriol will produce greater Amp-induced DA release relative to placebo, resulting in lower post-Amp, [¹¹C]-PHNO BP_{ND} values on calcitriol as compared to placebo days.

Specific Aim 4: To determine whether acute calcitriol (vs. placebo) pre-treatment is associated with better performance on a test of attention (e.g., the continuous Performance Task or CPT–IP), after treatment with amphetamine. **Hypothesis:** Similar to our hypothesis with healthy controls and congruent with our preliminary findings, we hypothesize that individuals with ADHD pre-treated with calcitriol will have faster reaction times/higher accuracy on the CPT–IP vs. subjects pre-treated with placebo, after treatment with amphetamine
2. **Background:** Describe the background information that led to the plan for this project. Provide references to support the expectation of obtaining useful scientific data.

[figure not shown]

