Data Analysis: The PET image sets are aligned and re-sliced to yield images in the same planes and spatial system as the MRI images using AAL template. A number of modeling approaches will be taken to quantitate binding potentials (BP_{ND}). Initially, the primary focus will be on reference region approaches, specifically the Simplified Reference Tissue Models (SRTM); i.e., time-activity curves will be fitted with the Simplified reference tissue model to extract binding potentials (BP_{ND}) in various brain regions.

Data Analyses: The primary outcome will be non-displaceable tracer binding potentials ($BP_{ND} = V_T - V_{REF} / V_{REF}$), which are linearly proportional to the density of available $D_{2/3}$ Rs, computed using a simplified reference tissue model (SRTM) utilizing the cerebellum as a reference region. This method has been previously validated. PET data will be reconstructed into images at Yale PET Center with all standard corrections using the appropriate reconstruction protocols and filters. All PET data will be reconstructed with an iterative reconstruction algorithm, MOLAR, designed specifically for the HRRT. MOLAR incorporates attenuation, scatter and deadtime, and subject-motion (detected by the Vicra system), into the forward projection model for the scanner. Emission images are binned into equal frame times (typically 3 minutes). Following image reconstruction, an early summed image (0-12 min) will be registered to the subject's MR image, which will be registered to an MR template so PET can be transformed to a standard (MNI) space. HYPR filtering will be applied to all emission data before analysis. Regions of interest will be the caudate, putamen, ventral striatum (VST), and substantia nigra / ventral tegmental area (SN/VTA). We will perform within-subject comparisons of the relative change in BP_{ND} elicited by calcitriol + Amp vs. placebo + Amp (ΔBP_{ND}), using appropriate parametric (paired t-) or non-parametric (Wilcoxon signed-rank test) tests. Although the proposed sample will enable detection of significant differences of moderate effect sizes ($d' = 0.59$) with a power of 0.8 and two-tailed alpha of 0.05, the sample will, at a minimum, provide estimates of effect size/power upon which future larger scales studies may be based. This effect size is congruent with preclinical work (Cass, Peters et al. 2012) and with clinical [^{11}C]-(+)-PHNO and [^{11}C]

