Raclopride studies (Shotbolt, Tziortzi et al. 2012). In secondary analyses, we will examine correlations (Pearson's) between cognitive (e.g., CPT-IP and PRLT), psychomotor (e.g., eye blink rate), and subjective (e.g., DEQ and simplified version of the amphetamine interview rating scale) measurements and neuroimaging outcomes/stimulant effects.

Statistical analyses will be the same for subjects with ADHD.

SECTION VI: RESEARCH INVOLVING DRUGS, BIOLOGICS, RADIOTRACERS, PLACEBOS AND DEVICES

If this section (or one of its parts, A or B) is not applicable, state N/A and delete the rest of the section.

A. DRUGS, BIOLOGICS and RADIOTRACERS

1. Identification of Drug, Biologic or Radiotracer: What is (are) the **name(s)** of the drug(s) biologic(s) or radiotracer(s) being used? Identify whether FDA approval has been granted and for what indication(s).

Radiotracer ([¹¹C]-PHNO): At the Yale PET center, we have characterized and applied an improved agonist radiotracer for the D2/3 receptor, [¹¹C]-PHNO, demonstrating its excellent test-retest variability in striatum (Gallezot et al., 2014b) and its greater sensitivity to Amp-induced DA release relative to traditional antagonist ligands (i.e., [¹¹C]-raclopride) (Shotbolt et al., 2012). As such, [¹¹C]-PHNO constitutes an optimal tracer for our proposed studies evaluating the effects of calcitriol on stimulant-induced DA release in humans. In addition, our group has considerable experience conducting such experiments with dextro-amphetamine challenges and [¹¹C]-PHNO in humans.

[¹¹C]-PHNO has been approved by the RDRC for use in previous human PET protocols at the Yale University PET Center. In addition, an IND was submitted to the FDA for the use of [¹¹C]-PHNO in another protocol at the Yale University PET Center. This IND was approved. We will add current protocol to that IND and we will also submit current protocol for approval by the Yale University RSC.

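### Aims 2 and 4 ask whether calcitriol improves CPT-IP performance over placebo, but Section V.12 plans only correlations for CPT-IP and no calcitriol-placebo comparison

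*Combined protocol and SAP*

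**What the plan says.** **Aims (Section V.1).** Aims 2 and 4 each ask whether calcitriol, against placebo, "pre-treatment is associated with better performance on a test of attention" once amphetamine has been given. Aim 2 predicts that "healthy human subjects pre-treated with calcitriol will have faster reaction times/higher accuracy" on the CPT-IP, and Aim 4 that "individuals with ADHD pre-treated with calcitriol will have faster reaction times/higher accuracy". Both make placebo pre-treatment the comparator.

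**Data collected (Section V.3, Test days and Table 1).** CPT-IP is run twice on each of the two test days: after the first scan, before the stimulant, and again after the second scan, after the stimulant. Both doses of study medication (the night before and that morning) precede the first session. The CPT-IP description in Section V.3 explains the task but names no score as the endpoint.

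**Analysis (Section V.12).** The one calcitriol-placebo comparison is: "We will perform within-subject comparisons of the relative change in BP_{ND} elicited by calcitriol + Amp vs. placebo + Amp", made by "using appropriate parametric (paired t-) or non-parametric (Wilcoxon signed-rank test) tests". CPT-IP appears in one sentence: "In secondary analyses, we will examine correlations (Pearson's) between cognitive (e.g., CPT-IP and PRLT), psychomotor (e.g., eye blink rate". The rest of that sentence adds the subjective ratings and pairs all these measures with imaging outcomes and stimulant effects. For the second cohort the section says: "Statistical analyses will be the same for subjects with ADHD". It also promises that "the sample will, at a minimum, provide estimates of effect size/power upon which future larger scales studies may be based".

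**The concern.** Two of the four numbered aims are about a mean difference between two treatment days, and the analysis section gives their outcome a method that does not look at mean differences. If the plan is followed to the letter, the report will contain no test of Aims 2 and 4 and no estimate of the calcitriol effect on attention. The promised minimum, effect-size estimates for later studies, would then be missing for CPT-IP.

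In practice the investigators would probably compare the two days anyway. The risk then is that the measure, and the test applied to it, are settled after the data are known. The aims join reaction time and accuracy with a slash and rank neither.

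**Working it through.** **1. The plan's own figure.** Section V.12 gives a detectable d' of 0.59 at power 0.80 and two-tailed alpha 0.05, stated directly after the binding-potential comparison. The normal approximation gives n = ((1.960 + 0.842)/0.59)² = 22.5. The exact paired t-test has power 0.790 at n = 24 and 0.808 at n = 25. Section V.5 recruits 30 per cohort with an unquantified allowance for losses, so 0.59 fits 24-25 completers. With all 30 the power would be 0.878. The figure is not in dispute, but it belongs to binding potential; no effect size is given for CPT-IP.

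**2. What a correlation can see.** For subject i let C_i and P_i be post-stimulant CPT-IP on the calcitriol and placebo days, and D_i = C_i − P_i. Aims 2 and 4 concern δ = E(D). Section V.12 does not say which values are correlated. Two natural readings are:
- Per-subject differences against imaging differences. Pearson's r uses D_i only through D_i − D̄. Adding any constant to every D_i leaves r and its p-value unchanged.
- One day's CPT-IP against that day's imaging. A constant shift in C_i again cancels.

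So r is the same whether δ is zero or large. In simulation (100,000 trials per case, n = 25 and 30), CPT-IP and imaging were independent within subjects and both shifted by 0.59 SD of the differences. Under either reading r was significant in 4.9-5.1% of trials, which is the nominal error rate.

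**3. What is fixed and what is open.**

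| Element | Status | Source |
|---|---|---|
| Contrast: calcitriol against placebo | fixed | Aims 2 and 4 |
| Direction: better on calcitriol | fixed | Aims 2 and 4 |
| Timing: after the stimulant | fixed | Aims 2 and 4 |
| Main measure: reaction time or accuracy | open | Aims 2 and 4 list both |
| Test | open | Section V.12 names tests for binding potential only |

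**4. Size of the open choice of measure.** Suppose there is no calcitriol effect, each measure gets a paired t-test at two-sided 0.05, and the better result is reported. If the two measures were independent:
- at least one p<0.05: 1 − 0.95² = 0.0975
- at least one in the hypothesised direction: 1 − 0.975² = 0.049

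Correlation between the measures lowers this. Simulated values, with 200,000 trials per case and bivariate normal within-subject differences (the correlations and completer numbers are assumptions):

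| Correlation | n = 25, any direction | n = 25, hypothesised | n = 30, any direction | n = 30, hypothesised |
|---|---|---|---|---|
| 0 | 0.098 | 0.049 | 0.096 | 0.049 |
| 0.5 | 0.092 | 0.045 | 0.092 | 0.046 |
| 0.8 | 0.078 | 0.039 | 0.079 | 0.040 |

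That is about 8-10% against 5%, or about 4-5% against 2.5% in the hypothesised direction, per cohort.

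**5. What a named paired test would give.** The 95% CI half-width is t/√n in SDs of the differences: 2.064/√25 = 0.41 and 2.045/√30 = 0.37. If d = 0.59 is borrowed from binding potential, power at 0.05 is 0.81 (n = 25) and 0.88 (n = 30). With both measures tested at 0.025 each, power per measure is 0.71 and 0.80.

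**The case against.** The strongest reply is that a paired comparison of the two days is plainly intended. The design is a within-subject crossover, the aims state the contrast, direction and timing, and binding potential is the declared primary outcome. Much of this stands, and it limits the point to a gap in non-primary aims. It does not close the gap: the paired tests are tied by their sentence to binding potential, and CPT-IP is then assigned a different method.

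A reader might infer more than the documents support:

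- **That post-stimulant value or change from the pre-stimulant session is equally open.** Counting two measures in two forms would raise the error to 14-18%, and letting the analyst take the better of t and Wilcoxon to 16-21%. But the aims specify performance after the stimulant, and the wording on tests reads most naturally as a choice by distribution, not by p-value. The figure for the choice of measure alone, 8-10%, is the one to use.
- **That correlations pooled over both days would partly do the job, or mislead.** The plan does not describe pooling, so figures for it say nothing about this trial.
- **That the sample is too small or too large for CPT-IP.** With no CPT-IP effect size and no evaluable number given, the 81-88% power is illustrative only.
- **That accuracy, or reaction time, is the right main measure.** The aims rank neither, and the choice belongs to the investigators.

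**Conclusion.** The point holds for Aims 2 and 4. As written, Section V.12 provides neither a test nor an estimate of the calcitriol-placebo difference in post-stimulant CPT-IP, in either cohort. This conclusion follows from the text and from the invariance of a correlation to a constant shift; it rests on no assumed number.

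The illustrated harm is moderate: a false-positive chance of about 8-10% per cohort in place of 5%, if the better measure is picked after the fact, there are 25-30 completers, and the measures correlate between 0 and 0.8. The primary binding-potential analysis is unaffected. The change should be made, but the trial's main result does not depend on it.

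**What to change.** Add to Section V.12 wording such as:

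*In each cohort, post-stimulant CPT-IP performance will be compared within subject between the calcitriol and placebo days by a two-sided paired t-test at 0.05, with the mean difference and 95% CI; Wilcoxon signed-rank is a sensitivity analysis.*

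Also state in advance:

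- **Measure.** Either name reaction time or accuracy as the main measure, with the other secondary, or test both at 0.025 each.
- **Change score.** Change from the same-day pre-stimulant session may be reported as supplementary, labelled as a different estimand. That session follows both calcitriol or placebo doses, so subtracting it removes any direct calcitriol effect on attention.
- **Correlations.** Keep the Pearson correlations as exploratory.

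The cost is a few sentences in the protocol. No visit, procedure or subject is added, because the CPT-IP sessions are already scheduled on both days. The drawback is that a benefit seen only on the measure not chosen counts as secondary. If both are tested at 0.025, power per measure falls to about 71% at 25 completers and 80% at 30, again using the borrowed d = 0.59.

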For the studies involving amphetamine, 30 research subjects participated, of whom 21 received two [¹¹C]-PHNO injections each, and 9 subjects received a single [¹¹C]-PHNO injection, for a total of 51 injections. Five subjects received a single injection of PHNO and did not receive amphetamine, and none experienced an adverse event. Twenty five subjects received both PHNO and amphetamine. No adverse events were experienced from the time immediately following the first PHNO injection (baseline) until amphetamine administration. Adverse events occurred in 6 of 25 subjects (24%), after amphetamine dosing. In 4 of the 6 subjects, the adverse event began 30–90 minutes after dosing with

amphetamine (4 of 25; 16%), but before the second PHNO administration. In 2 of the 6 subjects, the adverse event began approximately 3 hours after dosing with amphetamine (2 of 25, 8%), i.e., after the second [¹¹C]-PHNO. Adverse events reported on these 6 subjects were nausea/vomiting, dizziness, headache, epigastric pain, insomnia, psychosis, cardiac arrhythmia, hypertension, and psychosis.

Calcitriol: The frequency for potential side effects (e.g., please, see detailed description for these on section 9.5) of calcitriol is not well defined. There are certain circumstances that can increase the probabilities of adverse events, such as impaired kidney function, impaired liver function, high phosphorus, interaction with drugs/supplements that can increase calcium levels or that can cause complications in the setting of elevated calcium levels (e.g., cardiac glycosides), and vulnerability/recent history of kidney stones. There are studies using weekly doses of calcitriol among patients with malignancies. Each cycle consisted of 4 weekly administrations followed by 4 weeks of observation. Patients who tolerated each cycle proceeded to the next cycle up to weekly doses as high as 2 mcg/kg. This study revealed 8 instances of self-limited hypercalcemia and did not reveal toxicities requiring any medical intervention. As part of this study, authors proposed doses of 0.5 mcg/kg for phase II studies (Beer, Munar et al. 2001). There are also pharmacokinetic studies among healthy controls without any malignancies using intravenous or oral doses of 4 mcg and which did not show any significant side effects (Brandi, Egfjord et al. 2002). There are also studies among healthy controls using it at doses of 1.5 mcg/meter² of body surface area (N = 10) (Bianchi, Ardissino et al. 1999) or at doses of 3 mcg per day (N = 11) (Broadus, Erickson et al. 1984, Erickson, Cooper et al. 1984), which did not show significant side effects. The latter studies administered it for 10 consecutive days.

Subjects who have circumstances increasing risks of potential side effects will be excluded. In addition, we will monitor calcium levels as part of the study and we will have in place preventive actions that could decrease risks of potential side effects (e.g., modification of diet, higher intake of water, avoiding medications that could interact with calcium or calcitriol). We also preferred to split the total dose of 3 mcg in two different administrations of 1.5 mcg for ease of administration (e.g., three capsules will be easier than six), to maximize chances that [¹¹C]PHNO scans are conducted after calcitriol has worked (e.g., Onset of action after 2 hours; maximum effect after 10 hours; duration of effect is 3 to 5 days), and to maximize chances of subjects tolerating it.

Dexedrine: Most a complete list of potential side effects, please see section 9.6. Dexedrine is Clinically used in humans for treatment of ADHD and Narcolepsy at daily doses ranging from 5 to 60 mg. We have also experienced using it for our PET imaging studies with doses of 0.4 and 0.5 mg/kg. Proposed dose for this study of 0.3 mg/kg will be equivalent to 30 mg in a subject whose weight is 100 kg, thus within the doses FDA approved for therapeutic purposes. In terms of conditions increasing risks of side effects, subjects who have those will be excluded from the study. We will also monitor subjects throughout the study in order to early capture presence of any significant side effects (e.g., cardiovascular, psychiatric, or of any other nature). We will use the oral route due to the greater safety and ease of administration.

Taking into account that there are no studies administering calcitriol the same day as dextroamphetamine, we will use doses of each drug lower than the doses we have used before.

3. Source: a) Identify the source of the drug or biologic to be used.

[¹¹C]-PHNO prepared at the Yale PET Center.

Calcitriol capsules and Dexedrine tablets will be provided by the CMHC pharmacy.

b) Is the drug provided free of charge to subjects? Yes No
If yes, by whom?

4. Storage, Preparation and Use: Describe the method of storage, preparation, stability information, and for parenteral products, method of sterilization and method of testing sterility and pyrogenicity.

Check applicable Investigational Drug Service utilized:

YNHH IDS

Yale Cancer Center

CMHC Pharmacy

West Haven VA

PET Center

None

Other:

Note: If the YNHH IDS (or comparable service at CMHC or WHVA) will not be utilized, explain in detail how the PI will oversee these aspects of drug accountability, storage, and preparation.

Due to the short half-life, PET drugs are prepared and formulated immediately before administration, and therefore there are no issues with storage or stability. PET drug products are stored at room temperature and are stable for at least 60 min after preparation.

The preparation of sterile PET drug products is validated prior to human use. Sterility is achieved by passing the PET drug product through a 0.22 micron membrane filter during the last step in the formulation process. Prior to release for administration, a bubble point test is performed on the membrane filter used for terminal sterilization in order to validate and verify its integrity during the filtration process. Due to the short half-life, a sample of the PET drug product is tested for sterility after administration for further confirmation. The level of endotoxin in each batch of the final PET drug product is determined quantitatively prior to release for administration using the FDA approved Charles River Laboratory's Portable Testing System (Endosafe®-PTS).

[¹¹C]-PHNO will be prepared at the Yale PET Center in high radiochemical purity and high specific activity in accordance with our local Chemistry Manufacturing & Control (CMC) procedures and quality specifications described in local Drug Master File (DMF).

[¹¹C]-PHNO will be prepared at the Yale PET Center in high radiochemical purity and high specific activity in accordance with our local Chemistry Manufacturing & Control (CMC)

procedures and quality specifications described in local Drug Master File (DMF). Briefly, [¹¹C]propionyl chloride is prepared by reaction of [¹¹C]CO₂ with ethylmagnesium bromide, followed by treatment with phthaloyl dichloride. Then, *N*-acylation of the naphthoxazine precursor with [¹¹C]propionyl chloride, followed by reduction of the resulting [¹¹C]amide intermediate, yields [¹¹C]-PHNO. The resulting PET drug product is purified first by semi-preparative HPLC, followed by solid-phase extraction to remove the HPLC buffer mixture. Finally [¹¹C]-PHNO is formulated in <10% ethanolic saline solution (USP), and the resulting PET drug product is then passed through a 0.22 micron sterile membrane filter for terminal sterilization and collected in a sterile pyrogen free collection vial to afford a formulated I.V. solution ready for dispensing and administration.

5. Use of Placebo: Not applicable to this research project

If use of a placebo is planned, provide a justification which addresses the following:

1. Describe the safety and efficacy of other available therapies. If there are no other available therapies, state this.
- b. State the maximum total length of time a participant may receive placebo while on the study.
- c. Address the greatest potential harm that may come to a participant as a result of receiving placebo.
- d. Describe the procedures that are in place to safeguard participants receiving placebo.

6. Use of Controlled Substances:

Will this research project involve the use of controlled substances in human subjects?

Yes No *See HIC Application Instructions to view controlled substance listings.*

If yes, is the use of the controlled substance considered:

Therapeutic: The use of the controlled substance, within the context of the research, has the potential to benefit the research participant.

Non-Therapeutic: *Note, the use of a controlled substance in a non-therapeutic research study involving human subjects may require that the investigator obtain a Laboratory Research License. Examples include controlled substances used for basic imaging, observation or biochemical studies or other non-therapeutic purposes. See Instructions for further information.*

Dextro-amphetamine (0.3 mg/kg) will be given to each subject, by mouth, each experiment day, 2.5 hours after administration of calcitriol or placebo.

7. Continuation of Drug Therapy After Study Closure Not applicable to this project

Are subjects provided the opportunity to continue to receive the study drug(s) after the study has ended?

Yes If yes, describe the conditions under which continued access to study drug(s) may apply as well as conditions for termination of such access.

No If no, explain why this is acceptable.

SECTION VII: RECRUITMENT/CONSENT AND ASSENT PROCEDURES

1. Targeted Enrollment: Give the number of subjects:

- a. targeted for enrollment at Yale for this protocol 60 (30 per cohort)
- b. If this is a multi-site study, give the total number of subjects targeted across all sites Single-site

2. Indicate recruitment methods below. Attach copies of any recruitment materials that will be used.

 Flyers	 Internet/Web Postings	 Radio
 Posters	 Mass E-mail Solicitation	 Telephone
 Letter	 Departmental/Center Website	 Television
 Medical Record Review*	 Departmental/Center Research Boards	 Newspaper
 Departmental/Center Newsletters	 Web-Based Clinical Trial Registries	
 YCCI Recruitment database	 Clinicaltrials.gov Registry (do not send materials to HIC)	
 Other (describe): Word of mouth referrals; YCCI Facebook/Twitter		

*Requests for medical records should be made through JDAT as described at
<http://medicine.yale.edu/ycci/oncore/availableservices/datarequests/datarequests.aspx>

3. Recruitment Procedures:

- a. Describe how potential subjects will be identified.
 Subject will be recruited through the methods listed above such as flyers, radio adds, word of mouth referrals (see written material attached to protocol).
- b. Describe how potential subjects are contacted.
 Potential subjects will be encouraged to contact our study recruitment line for inclusion in our study.
- c. Who is recruiting potential subjects?

Subjects are recruited through our recruitment phone line. Subjects are asked to call in on our dedicated recruitment line. A member of our research staff will describe the study to participants who call, answer any questions the potential subjects has, and then complete a phone screening questionnaire to determine the subjects eligibility for an in-person screening visit. Subjects who are considered eligible based on this phone screening will be identified as potential participants therefore invited for the screening in person.

If an individual appears to meet enrollment criteria and is interested in participating, a face-to-face interview is conducted by the study staff and study physician. A release of information is obtained for review of any available historical and clinical data. A written authorization form is also obtained from each subject, permitting the research team to use, create, or disclose the subject's PHI for research purposes. The nature of the project, procedures, relative risks and benefits, and alternatives to participation in the project are discussed with the individual. Following this discussion, the individual is given a copy of the consent form to review, and any questions are answered. The process of informed consent will be obtained in accordance with

local IRB standards by study personnel who have participated in institutionally approved training in human subject protection. Upon obtaining voluntary, written, informed consent, medical and psychiatric screening procedures will be used to confirm study eligibility. Subjects are free to discontinue their participation in the research at any time.

4. Screening Procedures

- a. Will email or telephone correspondence be used to screen potential subjects for eligibility prior to the potential subject coming to the research office? Yes No
- b. If yes, identify below all health information to be collected as part of screening and check off any of the following HIPAA identifiers to be collected and retained by the research team during this screening process.

HEALTH INFORMATION TO BE COLLECTED:

HIPAA identifiers:

Names

All geographic subdivisions smaller than a State, including: street address, city, county, precinct, zip codes and their equivalent geocodes, except for the initial three digits of a zip code if, according to the current publicly-available data from the Bureau of the Census: (1) the geographic unit formed by combining all zip codes with the same three initial digits contains more than 20,000 people, and (2) the initial three digits of a zip code for all such geographic units containing 20,000 or fewer people is changed to 000.

Telephone numbers

Fax numbers

E-mail addresses

Social Security numbers

Medical record numbers

Health plan beneficiary numbers

Account numbers

All elements of dates (except year) for dates related to an individual, including: birth date, admission date, discharge date, date of death, all ages over 89 and all elements of dates (including year) indicative of such age, except that such ages and elements may be aggregated into a single category of age 90 or older

Certificate/license numbers

Vehicle identifiers and serial numbers, including license plate numbers

Device identifiers and serial numbers

Web Universal Resource Locators (URLs)

Internet Protocol (IP) address numbers

Biometric identifiers, including finger and voice prints

Full face photographic images and any comparable images

Any other unique identifying numbers, characteristics, or codes

Recruitment and screening procedures are the same for ADHD subjects.

5. Assessment of Current Health Provider Relationship for HIPAA Consideration:

Does the Investigator or any member of the research team have a direct existing clinical relationship with any potential subject?

Yes, all subjects

Yes, some of the subjects

No

If yes, describe the nature of this relationship.

6. Request for waiver of HIPAA authorization: (When requesting a waiver of HIPAA Authorization for either the entire study, or for recruitment purposes only. Note: if you are collecting PHI as part of a phone or email screen, you must request a HIPAA waiver for recruitment purposes.)

Choose one:

- For entire study
- For recruitment purposes only
- For inclusion of non-English speaking subject if short form is being used **and a translated HIPAA research authorization form is not available on the University's HIPAA website**

- i. Describe why it would be impracticable to obtain the subject's authorization for use/disclosure of this data;

The information we are collecting over the phone is required prior to the subject being considered for an in-person screening appointment. [REDACTED]

- ii. If requesting a waiver of **signed** authorization, describe why it would be impracticable to obtain the subject's signed authorization for use/disclosure of this data;

By signing this protocol application, the investigator assures that the protected health information for which a Waiver of Authorization has been requested will not be reused or disclosed to any person or entity other than those listed in this application, except as required by law, for authorized oversight of this research study, or as specifically approved for use in another study by an IRB.

Researchers are reminded that unauthorized disclosures of PHI to individuals outside of the Yale HIPAA-Covered entity must be accounted for in the “accounting for disclosures log”, by subject name, purpose, date, recipients, and a description of information provided. Logs are to be forwarded to the Deputy HIPAA Privacy Officer.

7. Required HIPAA Authorization: If the research involves the creation, use or disclosure of protected health information (PHI), separate subject authorization is required under the HIPAA Privacy Rule. Indicate which of the following forms are being provided:

- Compound Consent and Authorization form
- HIPAA Research Authorization Form

8. Consent Personnel: List the names of all members of the research team who will be obtaining consent/assent.

Consenting personnel is listed in IRES IRB.

9. Process of Consent/Accent: Describe the setting and conditions under which consent/assent will be obtained, including parental permission or surrogate permission and the steps taken to ensure subjects' independent decision-making.

All subjects will be consented through a multi-step consent process. Subjects are first described the study in detail over the phone during the phone screen. Health information such as medical, psychiatric, and substance use history, questions about presence of metal in their bodies, and information about current medications. If subjects are deemed appropriate from the phone screen, they are then invited to come the in-person screening appointment on the Clinical Neuroscience Research Unit. Consenting personnel will meet with the subject in person, explain both the consent form and the protocol and answer any questions the subject might have. The subject will be given a copy of the consent to read, at their leisure, prior to signing. Once the subject has signed the consent form the screening visit procedures will begin. This will take place at the Clinical Neuroscience Research Unit of CMHC.

Remote screening option: Subjects who pass telephone screening will be invited to a more in-depth screening to determine study eligibility (as listed in section on inclusion/exclusion criteria). Potential subjects who pass the phone screen portion will have the option to do the consenting screening portion remotely. They will be sent two copies of the consent form and a release of information to review at their leisure through a method that is most convenient for them (i.e., email, fax, or mail). This way subjects have time to review the consent prior to signing and they have their own copy to follow along and ask questions during the consenting phone call. If they agree to participate, subjects can keep one copy of the consent and hand-sign, date, and return the other copy along with a signed release of information back to our research office either by fax, email, or mail in a prepaid envelope. When the consent is also signed by a member of the research team, it will be filed in the subject's research record. Using tele-health platforms (i.e., Zoom) the researcher and subject will thoroughly review and sign the consent form, complete a structured clinical interview (SCID) by a member of the research team, and a medical history and psychiatric interview by a study physician. This will take up to two hours to complete in total. If deemed eligible by initial Zoom call and interviews, potential subjects will be asked to complete the rest of the study procedures as detailed in the protocol.

10. Evaluation of Subject(s) Capacity to Provide Informed Consent/Accent: Indicate how the personnel obtaining consent will assess the potential subject's ability and capacity to consent to the research being proposed.

We do not plan to recruit subjects with limited decision-making capacity. Potential subjects will undergo a phone interview and a face-to-face interview. At that time, the person obtaining consent will meet the study subject, review the informed consent form, explain the purpose of the study and risks associated with participation, and will be available for questions. Study staff is trained to assess the subject's understanding of pertinent information given to them and whether or not subjects can appreciate the implications of their decision. To ensure that the study subject understands the study, the subject will be asked questions about the study

procedures and the risks associated with participation. If any concern arises that the study subject did not fully understand the study, the person obtaining consent may decide that the subject is not suitable for participation. This process generally takes about 1 hour. If the subject is still interested, after all questions have been answered, the person obtaining consent will ask the subject to sign the informed consent form.

11. Documentation of Consent/Accent: Specify the documents that will be used during the consent/assent process. Copies of all documents should be appended to the protocol, in the same format that they will be given to subjects.

Compound consent and authorization form.

Process of consent form, evaluation of subject's capacity to provide informed consent, and documentation of consent will be the same for ADHD subjects.

12. Non-English Speaking Subjects: Explain provisions in place to ensure comprehension for research involving non-English speaking subjects. If enrollment of these subjects is anticipated, translated copies of all consent materials must be submitted for approval prior to use.

Non-English speaking healthy subjects nor ADHD subjects will not be enrolled in this study.

12(a) As a limited alternative to the above requirement, will you use the short form* for consenting process if you unexpectedly encounter a non-English speaking individual interested in study participation and the translation of the long form is not possible prior to intended enrollment?

YES NO

Note* If more than 2 study participants are enrolled using a short form translated into the same language, then the full consent form should be translated into that language for use the next time a subject speaking that language is to be enrolled.

Several translated short form templates are found on our website at: <http://www.yale.edu/hrpp/forms-templates/biomedical.html>. If the translation of the short form is not available on our website, then the translated short form needs to be submitted to the IRB office for approval via amendment prior to enrolling the subject. ***Please review the guidance and presentation on use of the short form available on the HRPP website.***

If using a short form without a translated HIPAA Research Authorization Form, please request a HIPAA waiver in the section above.

